7.3 Prohibited Medications

Use of the agents listed in Table 7-1 (prescription or nonprescription) is prohibited from the time points specified until completion of all study activities.

Table 7-1 Prohibited Medications

Medication or Class	Indication/Reason	From time point specified
antacids, anticoagulants, anticholinergics, antispasmodics, 5HT3 antagonists, dopamine antagonists, or opiates	Reduction/modification of GI motility	within 2 weeks of screening
oral or parenteral corticosteroids or topiramate, MAO inhibitors, growth hormone	Interference with glucose or insulin metabolism	within 3 months prior to screening.
Orlistat, lorcaserin, sibutramine	Weight control treatment, including over-the-counter and herbal medication and supplements, or any medication with a labelled indication for weight loss or gain	within 3 months prior to screening.
GLP-1 receptor agonists (e.g., exenatide, liraglutide, dulaglutide), dipeptidylpeptidase-4 (DPP-4), oral antidiabetic agents (e.g. SGLT2 inhibitors), insulin	Interference with glucose or insulin metabolism	any prior treatment
selective serotonin reuptake inhibitors (SSRIs), serotonin norepinephrine reuptake inhibitors (SNRIs), antipsychotics, lithium.	Depression, anxiety, or other psychiatric disorder	within 2 years of screening
Use of SSRIs and SNRIs (including bupropion) are allowed	If taken for reason other than active psychiatric indications [eg, migraine, weight loss, smoking cessation]	must meet a 3-month wash-out

7.4 Check in Criteria

Subjects will be educated about influencing factors, such as to refrain from strenuous exercise throughout the entire course of the study, to avoid alcohol and herbal supplements, (especially 24 hours prior to dosing), caffeinated drinks (caffeine containing

food and beverages 24 hours prior to dosing), smoking or medication and illness/infection.

At check-in for any in patient period(s), a subject will not be allowed to check in if they meet any of the following criteria and the treatment period may be rescheduled one time. The Sponsor will be notified about the rescheduling in a timely manner.

- 1. Positive alcohol breath test.
- 2. Positive urine drug screen test.
- 3. Positive urine pregnancy test in female subjects.
- 4. Any medical condition that could interfere with the study, as judged by the Investigator.
- 5. Any use of medicine other than any allowed concomitant medications within the last 24 hours.

8.0 STUDY MATERIALS

8.1 Investigational Products (IPs)

8.1.1 HM15211

A sterile solution of HM15211 contained in 0.52 mL pre-filled syringes will be provided. The concentration of HM15211 is 10 mg/mL as protein. HM15211 is manufactured by Hanmi Pharmaceuticals, Seoul, South Korea.

8.1.2 Placebo

Placebo is a sterile, matching solution (all components except drug substance) and free of visible particles. Placebo solution will be supplied in 0.52 mL pre-filled syringes by Hanmi Pharmaceuticals, Seoul, South Korea. Storage: 2 °C to 8 °C.

8.2 Packaging, and Labeling of Investigational Products

The Sponsor will provide the Investigator with the labeled IPs in accordance with specific country regulatory requirements.

The IP will be packaged and shipped to the clinical research unit (CRU) in an open label manner. Hanmi will prepare each syringe and place them in an independent paper box/carton.

8.3 Storage and Drug Accountability of Investigational Products

All clinical material will be kept in an appropriate, limited-access, secure location.

The investigational product, and its storage and preparation instructions, will be provided by the Sponsor. The IP must be stored securely at 2 °C to 8 °C (36 °F to 46 °F), and should not be exposed to excessive heat and never be frozen. It should be protected from direct sunlight and therefore should be kept in its carton until ready to be used.

HM15211 is stable at room temperature up to 4 hours.

The study staff is required to document the receipt, dispensing, and return/destruction of Study Drugs and supplies provided by or on behalf of the Sponsor. The CRU will destroy all used syringes of HM15211 and placebo at the CRU by the end of the study. Unused syringes of HM15211 and placebo will be processed as requested by the Sponsor by the end of the study.

The Investigator or Investigator's authorized staff must ensure the availability of proper storage conditions. The temperature of all study drugs will be monitored over 24 hours a day, 7 days a week (24/7). In case of incorrect storage, the Sponsor and monitor must be contacted without delay.

No study drugs may be dispensed to any person not enrolled in the study.

8.4 Dose Regimen

The IPs, HM15211 or placebo will be administered after an \geq 10 h overnight fast, by qualified staff while subjects are in the CRU. The products will be administered by SC injection into a lifted skin fold of the abdominal wall. The injection needle should be placed at a 45 to 90° degree angle and kept in the skin fold for 5-10 seconds. Aim is to dose at approximately the same clock time (eg, at approximately 08:00 h) for all subjects. The actual clock time of dosing is defined as t=0. The actual time of each dosing will be recorded in the source documents and on the eCRFs.

8.5 Overdose

If a study medication error occurs, it should be documented as Protocol Deviation. A brief description should be provided in the deviation, including whether the subject was symptomatic (list symptoms) or asymptomatic and whether the event accidental or intentional.

Dosing details should be captured on the Dosing Case Report Form. If the subject takes a dose of IP that exceeds protocol specifications and the subject is symptomatic, then the symptom(s) should be documented as an AE and be reported.

Should an overdose occur, the Investigator or designee should contact the Sponsor or designee within 24 hours.

8.6 Randomization and Blinding

To maintain the double-blind of the study, except for the unblinded persons involved in the preparation of the IPs (these persons are not involved in any other study activities), everyone involved in the trial will be blinded until after completion of the study and the final data review. Subjects will be randomized to IP or placebo in a ratio of 3:1 (6 subjects to IP, 2 subjects to placebo) prior to dosing.

Subjects will be randomized to treatment based on a randomization list that will be developed by a statistician. Individual treatment codes, indicating the treatment randomization for each randomized subject, will be available to the Investigator(s) or pharmacy staff at the CRU.

Subjects will be assigned to the lowest randomization number available. Subjects who withdraw prior to dosing on Day 1 may be replaced. If the replacement subject drops from the study, a second replacement subject may be enrolled. Subjects will be replaced at the end of the study following discussion between the Investigator and Sponsor.

The code for a subject may be broken in a medical emergency, if knowing the identity of the treatment allocation would influence the treatment decision of the subject or if demanded by the subject. Whenever a code is broken, the person breaking the code must record the time, date, and reason as well as his/her initials in the source documents. During un-blinding procedure in case of medical emergency, it should be ensured that no study personnel is unblinded to other subjects.

If the CRU need to break the code, the sponsor should, if possible, be contacted prior to breaking the blinding. In all cases, the Trial Monitor must be notified within 24 hours after an emergency un-blinding without revealing the treatment.

All codes (whether broken or not) must be kept throughout the trial period. Accountability of all broken or unbroken codes (hard copy or electronic) will be performed at or after trial closure and will be collected by the Monitor. A copy may be maintained in the Trial Master File (TMF).

The randomization code will include 4-digit subject numbers, 1001-1008 for the first cohort, 2001-2008 for the second cohort and follow the same numbering rationale for cohorts 3 through 5.

In case a subject need to be replaced, the replacement subject will receive the same treatment as the dropout subject. The replacement randomization numbers will have the second digit replaced (X1XX), for example subject 2101 will replace subject 2001 with the same treatment. If the replacement subject drops from the study, a second replacement subject may be enrolled with replacement number (X2XX). No replacement randomization list will be generated.

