6.3 Rationale for Study Design and Endpoints

This SAD study will assess the safety and tolerability as well as PK of HM15211 as primary objectives.

Cohorts will be assessed in ascending order, but may overlap, to determine a clinically appropriate dose for the subjects and will include the comparison with placebo.

Randomization is used to avoid bias introduced through an association between study drug allocation order and subject characteristics.

A double-blind design has been chosen to avoid bias and to maintain the blind between the administration of the study drug and placebo.

Healthy obese subjects will participate in the study, as these subjects are an important target population for the novel triple agonist. Enrollment criteria will favor the target population, as body mass index will be limited to ≥ 30 to ≤ 40 kg/m².

After PK modeling, C_{max} is expected to be reached approximately 3 days after dosing. As this is a first-in-human study, measurements for the assessment of cardiovascular events will start right after dosing and will continue until Day 4. After evaluation of the PK values in the initial cohort(s), the monitoring period will be adjusted, to ensure that the 24-h period around the PK_{peak} is captured.

The proposed PK endpoints are well-established, commonly used parameters to characterize pharmacological profiles of drugs. For the PK endpoints, blood samples for determination of HM15211 will be analyzed using a validated assay.

This is an exploratory study. No formal sample size calculation and no statistical hypothesis testing will be performed.

The study will be conducted at a specialized early phase research centre, where the subjects will be under supervision of physicians, research nurses and additional medical staff experienced in conducting early phase clinical studies investigating new metabolic compounds.

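### Section 8.6 lets a subject's code be broken at the subject's own demand, a ground not clearly tied to a medical emergency and without a time limit

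*Protocol*

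**What the plan says.** Section 8.6 first sets the blinding period. Apart from the staff who prepare the product, "everyone involved in the trial will be blinded until after completion of the study and the final data review". Section 6.3 gives the purpose: "A double-blind design has been chosen to avoid bias and to maintain the blind between the administration of the study drug and placebo".

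The code-break rule in 8.6 begins "The code for a subject may be broken in a medical emergency, if knowing the identity of the treatment allocation would influence the treatment decision" and then adds a second condition, so that the words after the mention of an emergency are "if knowing the identity of the treatment allocation would influence the treatment decision of the subject or if demanded by the subject". The rule is permissive (the verb is *may*) and concerns one subject's code. Whoever breaks a code must record the time, date, reason and initials.

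On access, "Individual treatment codes, indicating the treatment randomization for each randomized subject, will be available to the Investigator(s) or pharmacy staff at the CRU". On consultation, "the sponsor should, if possible, be contacted prior to breaking the blinding". On protecting the rest of the cohort, "During un-blinding procedure in case of medical emergency, it should be ensured that no study personnel is unblinded to other subjects". The 24-hour notice to the Trial Monitor is introduced as applying in all cases but is also worded for an emergency unblinding.

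**The concern.** A code-break rule is a necessary exception to the blind, and it is normally justified by clinical need. Here a second ground stands beside clinical need and asks only that the subject wants to know. Nothing says at what stage of the study it may be used or who must agree.

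The outcomes most exposed are the subjective ones. Adverse events are a primary endpoint (5.1), are partly elicited by a non-specific question to the subject (10.4.1), and are classed for relatedness by the Investigator's clinical judgment (10.3). Subjects who feel unwell, or who notice nothing, are plausibly the likeliest to ask, so the loss of blinding could be related to outcome. In a cohort of eight, one judgment of relatedness can also decide whether escalation continues.

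**Working it through.** The protocol gives no figure on this point and plans no hypothesis test (6.3). The check compares the wording and then makes a short count.

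**1. Two readings of the sentence.**
- Reading A: the emergency governs both conditions. A demand then counts only in an emergency, but it still suffices when knowing the allocation would not affect treatment, because the two conditions are joined by *or*.
- Reading B: the demand is a separate ground that needs no emergency.

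The sentence protecting other subjects specifies an unblinding in a medical emergency, which suggests that other unblindings are foreseen and favours B. The Monitor sentence equates all cases with emergency unblinding, which favours A. B is the more natural reading, but the text does not settle it. On both readings a code may be opened when the allocation would not change treatment.

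**2. Safeguards for a break on demand.**
- Record of time, date, reason and initials: covers any break.
- Sponsor contact: asked for if possible, and not an approval step.
- Protection of other subjects' allocation: worded for a medical emergency.
- Monitor notice within 24 hours: worded for an emergency unblinding.

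The last two do not clearly reach a break on demand.

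**3. Timing.** Subjects leave the unit on Day 7 and return on Days 10, 17 and 30 (6.2). Adverse events are collected to the follow-up visit (10.4.1). From discharge to nominal follow-up is 30 − 7 = 23 days. The escalation decision can be made once at least 6 subjects, at least 4 of them on active drug, have completed Day 10 (4.5). The demand ground has no time limit, so a code could be opened before that decision, and at any time before the Day 30 assessments.

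**4. Route to the stopping criteria.** Under 6.4.1, escalation stops if one subject in a cohort has an event of Grade 3 or higher, or a Grade 2 event lasting more than 7 days, that the Investigator judges related. If the Investigator has opened or learned the code, that judgment is no longer blind.

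**5. What one opened code reveals.** Inputs: 8 subjects per cohort, 6 active and 2 placebo, with a sentinel pair of 1 active and 1 placebo (6.1). The other six are therefore 6 − 1 = 5 active and 2 − 1 = 1 placebo.

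| Code opened | Share of the 8 | Others identified with certainty |
|---|---|---|
| Either sentinel | 2/8 | 1 (the partner) |
| Placebo among the other six | 1/8 | 5 (all active) |
| Active among the other six | 5/8 | 0 |

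Chance of identifying at least one other subject = 2/8 + 1/8 = 3/8 = 37.5%. In the last row, the chance that each of the remaining five non-sentinels is active moves only from 5/6 (83%) to 4/5 (80%).

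Separately, 8.6 gives a replacement the same treatment as the dropout under a linked number. An opened dropout code therefore discloses the replacement's allocation. This is not included in the 3/8.

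**The case against.** The strongest reply is that the sentence begins with a medical emergency, and that this can govern everything after it. That reading is grammatically open and the Monitor sentence supports it. It narrows the problem without removing it, because a demand would still replace clinical relevance as the reason for opening the code.

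A reader might also infer more than the text supports:
- *A subject is entitled to the code on request.* The rule says that the code may be broken, not that it must be.
- *No medical need is required.* That is reading B, which is more natural but not established.
- *Any participant can end the double-blind.* The rule opens one subject's code. The study blind remains, although others may be identified by deduction.
- *The rule flatly contradicts the blinding statement.* Any code-break rule is an exception to it, including the emergency ground. The difficulty is an exception that is not clearly limited to clinical need.
- *The 3/8 measures the harm of the demand ground.* It is conditional on a code being opened, assumes that each of the eight is equally likely, and applies equally to an emergency break. Deleting the demand ground would not change it.

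Other points for the defence stand. Many primary endpoints are measured (laboratory values, QTcF, ABPM, Holter, PK), so knowledge of the allocation affects them less. The study is exploratory and descriptive. Every break is documented, so affected subjects can be identified. Codes are available to the Investigators or to pharmacy staff, so the assessing Investigator need not be the one who opens the code. None of this protects the subject's own reporting, or a relatedness judgment by an Investigator who does learn the allocation.

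**Conclusion.** The point holds in limited form. Section 8.6 allows a code to be opened for a reason other than clinical relevance, on either reading of the sentence. It does so without a time limit and without clear cover from the two safeguards worded for emergencies. The exposure is confined to that subject's adverse event reports and relatedness judgments, plus any other subjects whose allocation can be deduced.

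The consequence is moderate. No hypothesis test is at risk, but a single relatedness judgment can stop escalation. The documents give no basis for estimating how often subjects would ask, so the expected number of affected subjects is unknown. The 3/8 describes what follows one opened code, assuming equal likelihood, a full cohort of eight and knowledge of who the sentinels were. The clause should be changed. It is a rule of trial conduct, so it is for the protocol to settle and not for a statistical analysis plan.

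**What to change.** In section 8.6, delete the subject's demand as a ground for breaking the code during the study and leave the medical-emergency ground as it stands. Add that a subject who asks is told the allocation after study completion and final data review, which matches the blinding period already set in that section.

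This removes the need to choose between the two readings. With only the emergency ground left, the safeguard for other subjects and the Monitor notice, as now worded, cover every permitted break.

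The cost is a one-sentence amendment and matching consent wording where needed. The only downside is that a subject who asks must wait for the answer.

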6.0 STUDY DESIGN AND DESCRIPTION

6.1 Study Design

This is a first-in-human, randomized, double-blind, SAD study to evaluate the safety, tolerability, and PK of HM15211 as primary objectives in healthy obese subjects.

The study will be conducted in five sequential cohorts (cohort 1 to 5) comprising a total of up to approximately 40 subjects. Each cohort will enroll subjects to ensure that at least 8 subjects per cohort will complete the study. Drop-outs may be replaced in order to have 8 completed subjects in each cohort. Subjects will be allocated into sequential dosing cohorts based on their order of entry into the study and be randomized to investigational product (IP) or placebo in a 3:1 ratio, with 6 subjects on IP and 2 subjects on placebo. Cohorts may partially overlap after at least 6 subjects have completed at least D10 and a dose escalation decision has been made.

Dosing will follow a sentinel approach with the dosing between the first 2 subjects (1 on active, 1 on placebo) and the remainder of the cohort at least 24 hours apart. A minimum of 10-days between the start date of consecutive dose levels will be maintained. Based on available safety, tolerability, and PK data of each cohort, and following a safety review and dose escalation meeting between the investigator and the sponsor, dose escalation to the next cohort may proceed. If dose escalation is stopped (please see dose escalation stopping criteria in section 6.4.1), dose de-escalation may occur in additional cohorts, to further refine clinically relevant dose levels.

Each subject will undergo a screening visit, followed by one in-house/ treatment period per subject. Two additional outpatient visits will occur, prior to a final follow-up visit that will conclude subject study participation.

The duration of subject participation in this study, including screening, treatment and follow-up will approximately be 9 weeks for subjects.

Figure 6-1 Study Design Schematic

[figure not shown]
[figure not shown]

Figure 6-2 Dose Escalation Schematic

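### Section 8.6 gives a replacement the drop-out's treatment under a linked number with no exception after a code break, so whoever learned that code knows the replacement's arm

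*Protocol*

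**What the plan says.** Protocol section 8.6 contains five rules that bear on each other.

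- **Replacement arm.** The protocol says "the replacement subject will receive the same treatment as the dropout subject". The link is visible in the number: "for example subject 2101 will replace subject 2001 with the same treatment". A second replacement takes an X2XX number in the same way, and "No replacement randomization list will be generated".
- **Code breaks.** Medical emergencies are the setting in which a code may be opened, and the condition reads "if knowing the identity of the treatment allocation would influence the treatment decision of the subject or if demanded by the subject".
- **Limit on an emergency break.** During emergency un-blinding, "it should be ensured that no study personnel is unblinded to other subjects".
- **General blind.** Apart from the people who prepare the product, "everyone involved in the trial will be blinded until after completion of the study and the final data review".
- **Who is replaced.** Section 8.6 names subjects who withdraw before dosing on Day 1. It then allows a second replacement if the first one drops out, without repeating the pre-dose limit. It places replacement at the end of the study, after the Investigator and Sponsor have discussed it.

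Section 6.1 is wider on the last item: "Drop-outs may be replaced in order to have 8 completed subjects in each cohort". Nothing in either section says what happens to the replacement rule when the drop-out's code has been opened.

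**The concern.** The same-treatment rule and the linked number are harmless while the drop-out's allocation stays concealed. Once it has been disclosed, the rule turns knowledge about one subject into knowledge about the next, who has not yet been dosed or assessed.

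This matters because much of the primary safety assessment is judgement. Relatedness (10.3) and the reading of the ECGs (9.1.11) belong to the Investigator or a designee, and injection-site scoring (9.1.19) is done at the site. The trial has a single site, and 8.6 makes the individual codes available to the Investigator(s) or pharmacy staff there. The person who learned a broken code may therefore be the person who assesses the replacement. That subject would be assessed open-label, but the data would enter the dose group or the pooled placebo as if blinded.

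**Working it through.** **Inputs.** Five cohorts of 8, randomized 6:2 (sections 2.0, 6.1 and 8.6); the same-treatment rule and linked numbers (8.6); placebo pooled across cohorts for safety and PD (12.2.4, 12.2.5). The plan's own figures reproduce: 5 × 8 = 40 subjects and 6/2 = 3, which is the stated 3:1 ratio. No alpha, power or effect size enters.

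**Step 1: what a blinded person knows.** The probability that a given replacement is on active is 6/8 = 0.75. Section 6.1 starts each cohort with a sentinel pair, one active and one placebo. Someone who knows the dosing order would use 1/2 for a sentinel position and 5/6 = 0.83 for the rest. These average to (2 × 1/2 + 6 × 5/6)/8 = 6/8, so 0.75 is right over the cohort.

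**Step 2: what a person who learned the drop-out's code knows.** The number 2101 points to 2001, and the rule makes the arms equal. The probability of active becomes 1 if 2001 was on active and 0 if on placebo, whatever the starting value. The same holds for 2201 if the chain goes on.

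**Step 3: is this special to replacement?** Opening one code always says something about the rest of the cohort. From the 6:2 total alone, another original subject moves from 0.75 to 5/7 = 0.71 (opened code active) or 6/7 = 0.86 (opened code placebo). Those two figures ignore the sentinel pairing, under which the partner of an opened sentinel is known as well. The point does not rest on this contrast. What sets the replacement apart is that it is enrolled after the disclosure, so the exposure can be avoided.

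**Step 4: can the sequence occur under the text?**

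| Rule followed | Replaceable subjects | Code break before replacement |
|---|---|---|
| 8.6, first replacement | Withdrawals before dosing on Day 1 | Remote: 6.2 places randomization as close to dosing as possible |
| 8.6, second replacement | A first replacement who drops out; no pre-dose limit repeated | Possible |
| 6.1 | Drop-outs generally, up to 8 completers | Possible: covers losses after dosing |

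Section 6.4.3 lists adverse events and withdrawal of consent among the reasons for leaving. A subject who demands the code and then withdraws would reach this situation without an emergency.

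**Step 5: size.** One affected active replacement is 1/6 = 17% of the planned active subjects at that dose. One affected placebo replacement is 1 of 5 × 2 = 10 in the planned pool, or 10%. If the drop-out had already been dosed, it stays in the Safety set (12.2.1.1) and the shares there fall to 1/7 = 14% and 1/11 = 9%.

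**Step 6: what a general change of the rule would cost.** If replacements were drawn afresh at 3:1, the 6:2 split among completers would survive one replacement with probability 0.75² + 0.25² = 0.625. Under the same-treatment rule it survives with probability 1.

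**The case against.** The strongest reply is that the text can be obeyed in full. Replacement is worded as permitted, not required, and follows a discussion between Investigator and Sponsor, so they can simply decline to replace a subject whose code was opened. That stands. A reader might infer that the two rules of 8.6 cannot both be followed; the documents do not support this. The gap is a missing exception. It still matters, because 6.1 sets 8 completers as the aim of enrolment and nothing warns against the linked replacement.

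Other stronger readings also fail:

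- **That 8.6 expressly forbids this case.** The sentence on other subjects is worded for emergency un-blinding, and naturally means that opening one code must not expose others. A later replacement is not yet a subject, and a break on demand is outside that sentence. The conflict is with the general blinding sentence.
- **That the replacement is unblinded to everyone.** Only those who learned the code are affected. The Trial Monitor is told of an emergency break without the treatment, and the linked number alone reveals nothing.
- **That dose escalation is compromised.** Several stopping criteria in 6.4.1 do rest on the Investigator's causality call. But 4.5 lets escalation proceed on 6 subjects with at least 4 on active, and 8.6 places replacement at the end of the study, so replacements would often come after the decision.
- **That subjects with emergencies leave more often and so are replaced more often.** The documents give no basis for this, and after a single dose there is no further treatment to discontinue.
- **That same-treatment replacement should be dropped altogether.** Where no code was opened it reveals nothing, and it keeps 6:2.

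**Conclusion.** The concern holds as a latent gap in 8.6. If a subject's code is opened to otherwise blinded staff and that subject is replaced as the section prescribes, those staff know the replacement's arm with certainty, contrary to the section's general blinding rule. The inference is deterministic; how often it would arise is not known from the documents, and it needs both events. It is remote if only withdrawals before dosing are replaced, and a practical possibility under 6.1, so the difference between 6.1 and 8.6 on who may be replaced is part of the problem.

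The effect is limited to judgement-based safety assessments in one subject per occurrence, or two if the chain reaches X2XX. It assumes that someone who learned the code also assesses the replacement or takes part in decisions about it, which is plausible at a single site but not stated. Assay-based PK endpoints are little affected, and no hypothesis test is planned (6.3). This is a cheap improvement to make, not a fault that undermines the trial.

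**What to change.** 1. Add to 8.6 that a subject whose code has been broken to otherwise blinded site or sponsor staff is not replaced under the linked same-treatment rule. Apply this at each link, so that a code break on an X1XX subject also rules out an X2XX replacement.
2. Reconcile 6.1 and 8.6 on who may be replaced: withdrawals before dosing only, or drop-outs at any time. State whether the same limit applies to the second replacement.
3. Keep same-treatment replacement for all other drop-outs, because it preserves 6:2.

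The cost is one amendment sentence and one clarification. A cohort with a code break may finish with 7 completers instead of 8, so the aim of 8 completers in 6.1 should allow for this case. Section 12.4 describes the cohort size as empirical, so no power calculation is disturbed.
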